### **1.1.1 PRECLINICAL STUDIES WITH FLUORESCEIN**

Murine tumors have been investigated with the use of intravital microscopy in an attempt to evaluate blood vessel characteristics, blood flow patterns, and interactions with immune cell subsets.[1, 7, 9] Fluorescein conjugated to Dextran has been employed for several intravital microscopy studies[1, 15] and allows for a more precise assessment of the tumor vasculature[1, 7].

Preclinical laboratory studies have established that fluorescein can be used to image the microvasculature in B16 mouse melanoma tumors in the similar doses used clinically. Fluorescein is not expected to have a direct intervention on tumor biology. The ability to study tumor microvasculature by using IVM does not require a window chamber, and human IVM techniques have provided highly reproducible and consistent measurements. There have been several published animal studies which have demonstrated IVM of the lymphatic system in addition to blood vessels.[10, 16]

### 1.1.2 CLINICAL STUDIES WITH FLUORESCEIN

This protocol intends to apply the commonly used intraoperative fluorescent agent, fluorescein, to further characterize blood vessels associated with deep space solid tumors. It is anticipated that fluorescein will be readily detectable in the microscopic field of observation following intravenous fluorescein injection.

Fluorescein is not expected to have a direct intervention on tumor biology. Fluorescein is routinely used during the course of surgery for a variety of indications (e.g. intraoperative assessment of bowel or organ perfusion, vessel angiography of the retina) and is deemed non-toxic with no long term side effects.

Clinically, fluorescein is most commonly used for ophthalmologic procedures including fluorescein angiography with intravenous injection. Fluorescein angiography is performed by injecting fluorescein sodium dye as a bolus into a peripheral vein. The normal adult dosage is 500 mg, and is typically packaged in doses of 5 mL of 10% or 2 mL of either 10 or 25% concentration. For pediatric patients, the dose is adjusted to 35 mg per 10 pounds of body weight.[17]

Upon entering the circulation, approximately 80% of the dye molecules bind to plasma proteins, which significantly reduces fluorescence because the free electrons that form this chemical bond are subsequently unavailable for excitation.[18] The remaining unbound or free fluorescein molecules fluoresce when excited with light of the appropriate wavelength. With a molecular weight of 376, fluorescein diffuses freely out of all capillaries except those of the central nervous system, including the retina.

The dye is metabolized by the kidneys and is eliminated through the urine within 24 to 36 hours of administration. During this period of metabolism and elimination, fluorescein has the potential to interfere with clinical laboratory tests that use fluorescence as a diagnostic marker.[19, 20] To avoid any false readings, it may be prudent to schedule clinical lab tests either before the angiogram, or postpone testing for 1 or 2 days to allow sufficient elimination of the dye. Side effects of intravenous fluorescein include discoloration of the urine for 24 to 36 hours and a slight yellow skin discoloration that fades within a few hours. Nursing mothers should be cautioned that fluorescein is also excreted in human milk,[21] for this reason, nursing mothers will be excluded from this study.

Use of fluorescein sodium may be contraindicated in patients with history of allergic hypersensitivity to fluorescein. Although generally considered safe for patients receiving dialysis, one manufacturer of fluorescein suggests using half the normal dose in dialyzed patients.[22] There are no known risks or adverse reactions associated with pregnancy, but most practitioners avoid performing fluorescein angiography in pregnant women, especially in their first trimester.[23-25]

Historically, adverse reactions occur in 5% - 10% of patients and range from mild to severe.[27-32] Anecdotal evidence suggests a lower incidence of reaction in recent years and the first large study conducted in over a decade seems to confirm that, reporting a frequency of adverse reaction of just over 1%. [33] Continued improvements in manufacturing processes and implementation of tighter pharmacopeial standards are credited with this reduction and may lead to lower rates of reaction in the future.[34]

Transient nausea and occasional vomiting are the most common reactions and require no treatment. These mild reactions typically occur 30 – 60 seconds after injection and last for about 1 to 2 minutes. Fortunately, they seldom compromise the diagnostic quality of the angiogram. The incidence of nausea and vomiting seems to be related to the volume of dye and rate of injection. A relatively slow rate of injection often reduces or eliminates this type of reaction but can adversely affect image quality and alter arm-to-retina circulation times. Premedication with promethazine hydrochloride or prochlorperazine may prevent or lessen the severity of nausea and vomiting in patients with a history of previous reactions to fluorescein, but is rarely needed and one study noted a higher frequency of these reactions in patients that had been premedicated.[30] Some patients report a strong taste sensation or hypersalivation following injection of fluorescein.

Moderate reactions occur less frequently, affecting less than 2% of patients that undergo angiography. Allergic reactions such as pruritus or urticaria can be treated with antihistamines, but any patient who experiences these symptoms should be observed carefully for the possible development of anaphylaxis. The advisability of performing angiograms in patients with a history of allergic reaction to fluorescein should be considered carefully, as allergic sensitization to the dye can increase with each subsequent use. Patients with previous history of mild allergic reaction to fluorescein can be pre-treated with an antihistamine, such as diphenhydramine, 30 - 40 minutes prior to any subsequent angiograms to limit allergic response, although this may not prevent serious reactions.[35]

More severe reactions are rare, but include laryngeal edema, bronchospasm, anaphylaxis, tonic-clonic seizure, myocardial infarction, and cardiac arrest.[36-40] The overall risk of death from fluorescein angiography has been reported as 1 in 222,000 due to anaphylaxis.[30] Although life-threatening reactions during angiography are rare, angiographic facilities and personnel should be properly equipped and prepared to manage serious reactions to the procedure. A resuscitative crash cart and appropriate agents to treat severe reactions should be readily available including epinephrine for intravenous or intramuscular use, soluble corticosteroids, aminophylline for intravenous use, oxygen, and airway instrumentation. It is generally recommended that a physician be present or available during angiographic procedures.

Extravasation of fluorescein dye during the injection can be a serious complication of angiography. With a pH of 8 to 9.8, fluorescein infiltration can be quite painful. If fluorescein dye extravasates, cold compresses should be placed on the affected area for 5 to 10 minutes, and the patient should be reassessed until edema, pain, and redness resolve. Serious complications are more likely to occur when large amounts of dye extravasate. Sloughing of the skin, localized

necrosis, subcutaneous granuloma, and toxic neuritis have been reported following extravasation of fluorescein.[41-43] To avoid these problems, continual observation of the injection site during the course of the injection and monitoring the patient for pain is recommended. Accidental arterial injections are rare, but can be quite painful. The dye remains concentrated and stains the effected extremity with little or no dye reaching the retinal vasculature. With proper technique, these complications of injection can usually be avoided.

## 1.2 RISKS AND/OR BENEFITS

**Risks** – low risk of allergic reaction to fluorescein as described above. Otherwise, no increased risk of surgical procedure anticipated.

**Benefits** – depending upon collected findings and correlation with clinical outcome, HIVM may offer prognostic information and potentially guide treatment decisions in the future.

## 2 RATIONALE

These studies will elucidate the hemodynamic properties of microvessels associated with deep space solid tumors. In order to model the effects of tumor-associated vessel function on patient outcomes, direct examination of the microvasculature in these patients is necessary to ascertain if the preclinical model systems have accurately recapitulated the clinical setting. Thus, the current proposed trial represents an opportunity to support the development of interventions to improve patient treatment by extending the application of IVM to the locoregional tumor microenvironment. In addition, by adding HIVM observations during the course of volume and pressor management during the course of surgery, further data regarding tumor vessel dynamics will be obtained, which may offer a means to augment responses to systemic treatments.

## 3 OBJECTIVES

### 3.1 PRIMARY OBJECTIVE - PART I (10 PATIENTS):

To determine the feasibility of performing HIVM in patients with deep space solid tumors during the standard course of surgical treatment (resection). A successful intravital microscopic observation will include the ability to complete each of the following:

1. Identify and measure vessels associated with tumor
2. Determine vessel density per 10x field
3. Visualize vital dyes within the vessels (fluorescein)
4. Calculate the blood flow velocity of the vessels and tissue penetration of as a marker of vessel permeability.

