*Primary objective(s):* To determine the feasibility of performing HIVM in patients with deep space solid tumors during standard course of surgical resection. A successful intravital microscopic observation will include the ability to complete each of the following:

1. Identify and measure vessels associated with tumor
2. Determine vessel density per 10x field
3. Visualize vital dyes within the vessels (fluorescein)
4. Calculate the blood flow velocity of the vessels and tissue penetration of fluorescein as a marker of vessel permeability.
5. Obtain these vessel parameters after administration of an IV fluid bolus and/or vasopressor administration (phenylephrine or vasopressin) during the normal course of the surgical resection.

*Secondary objective(s):*

1. Compare the microscopic observation of the tumor-associated vessels with normal tissue (e.g. peritoneal surface) in each individual subject.
2. Correlate the microscopic observations of the tumor-associated vessels with pathologic grade of tumor.
3. To correlate the microscopic observation of the microvasculature with tumor-specific and overall survival.

Study Design: This is a non-randomized, single center, study of HIVM observation in subjects with deep space solid tumors undergoing surgical resection.

All subjects will meet the inclusion and exclusion criteria prior to participation in this study. Standard evaluation by the Preoperative Anesthesia clinic at Mayo Clinic Florida may include additional testing such as EKG, chest x-ray, and/or pulmonary function tests.

The study will be performed in two parts. Part 1 will enroll 10 patients with an expected feasibility rate of 70%. Whereas the feasibility rate in primary melanoma was 90%, the expected feasibility rate for deep space tumors may be lower as the site is in an anatomically deeper location. If Part 1 is not met (i.e. in three or more patients), the primary objective would not be considered technically feasible, and then the study will be stopped. If Part 1 is fulfilled, then the study will continue with an additional 40 patients enrolled (total of 50 patients). Accrual is expected to take 2.5 years.

*Inclusion criteria:*

1. Age  $\geq$  18 years of age.
2. ECOG Performance Status of  $\leq 2$ .
3. Measurable tumor by direct visualization requiring surgical resection in the OR.

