### 3.2 SECONDARY OBJECTIVES - PART II (40 PATIENTS):

1. Compare the microscopic observation of the tumor-associated vessels with normal tissue (peritoneal surface) in each individual subject.
2. Correlate the microscopic observations of the tumor-associated vessels with pathologic grade of tumor.
3. To correlate the microscopic observation of the microvasculature with tumor-specific and overall survival.

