## **TARGET ACCRUAL AND STUDY DURATION**

A maximum of 50 subjects [Part I (10 patients) and Part II (40 patients)] will be enrolled. The number of subjects required is a function of the expected feasibility. Accrual is expected to take up to 2.5 years.

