## **9 STATISTICAL METHODOLOGY**

Initially ten patients will be treated to determine the feasibility of HIVM for deep space tumors. This first part of the study is a pilot study of feasibility. If seven or more patients are deemed a success by meeting all of the criteria below, then HIVM will be deemed feasible in the study of deep space tumors. Criteria include the ability to complete each of the following:

1. Identify and measure vessels associated with tumor
2. Determine vessel density per 10x field
3. Visualize vital dyes within the vessels (fluorescein)
4. Calculate the blood flow velocity of the vessels and tissue penetration of fluorescein as a marker of vessel permeability.

If the true success rate is 60%, the probability of deeming HIVM feasible is 63%; if the true success rate is 70%, then the probability of deeming HIVM feasible is 88%; and if the true success rate is 90%, then the probability of deeming HIVM feasible increases to 99%.

If HIVM is deemed feasible, then an additional 40 patients will be accrued to this study in order to address the following:

1. Post-operative comparison of the microvasculature of tumor with normal tissue (peritoneum) in each individual subject using vessel diameters, vessel density, detection of intravital dye and flow rates.
2. Post-operative correlation of the microvasculature with pathologic features of the tumor (i.e. tumor grade) at the time of the final pathology report (5-7 days after surgery).
3. Post-operative correlation of the microscopic observation of the tumor microvasculature tumor-specific and overall survival.

An abnormal HIVM observation is defined by any of the following criteria:

1. Aberrant vessel structure compared to normal tissue, which includes tortuosity of the vessel wall or a closed loop formation.
2. Aberrant vessel branching patterns compared to normal tissue, which includes erratic and disorganized branching points.
3. Blood vessel density that is less than or greater than one standard deviation of the blood vessel density observed in normal tissue.
4. Inability to detect flow or fluorescein within a vessel.
5. Average blood flow rate through observed vessel that is less than one standard deviation of the average blood flow rate through a normal vessel.

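### Feasibility is settled by a 7-of-10 rule with no success proportion or confidence interval planned, although the same endpoint can be scored in the 40 Part II patients

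*Combined protocol and SAP*

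**What the plan says.** Section 3.1 is headed "PRIMARY OBJECTIVE - PART I (10 PATIENTS" and Section 3.2 "SECONDARY OBJECTIVES - PART II (40 PATIENTS". Section 9 follows the same division. It opens with "Initially ten patients will be treated to determine the feasibility of HIVM for deep space tumors" and then gives the rule: "If seven or more patients are deemed a success by meeting all of the criteria below, then HIVM will be deemed feasible". The expansion has a different purpose: "If HIVM is deemed feasible, then an additional 40 patients will be accrued to this study in order to address the following". The list that follows covers tumor versus normal tissue, association with tumor grade, and association with survival. Feasibility is not on it.

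The only confidence limits that Section 9 plans for a rate are one-sided Clopper-Pearson limits for adverse events and complications.

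The endpoint itself is wider than Part I. Section 3.3 defines success for each patient by four measurements, without naming a part. Section 4.2 describes the imaging and off-line measurement once, for all subjects, and notes that the stored data are enough to judge whether an observation succeeded. The accrual section gives the total: "A maximum of 50 subjects [Part I (10 patients) and Part II (40 patients)] will be enrolled".

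**The concern.** Section 9 uses the first ten patients for two purposes. One is to decide whether to continue, which a small pilot can do. The other is to pronounce the technique feasible in deep space tumors, which is the trial's primary question. The second is a statement about a rate, but the plan attaches neither an estimate nor an interval to it, and nothing seen in Part II can revise it. Suppose 7 of 10 succeed in Part I and 20 of 40 in Part II. Overall success is (7 + 20)/50 = 54%, yet the planned primary conclusion would remain the one reached at patient ten.

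What is at stake is how precisely the primary result is known, and whether its denominator and interval are fixed in advance. If investigators report a 50-patient rate without having planned it, those choices will be made after the data are seen.

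**Working it through.** **Inputs.** Part I has n = 10 and passes at 7 or more successes (Section 9). Part II adds 40, for a maximum of 50 (accrual section). The expected rate is 70% (synopsis: "Part 1 will enroll 10 patients with an expected feasibility rate of 70" percent). The plan gives no confidence level for feasibility, so two-sided 95% is my assumption.

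**1. The plan's own figures.** Section 9 states the probability of a feasible verdict at three true rates p. The exact value is P(X ≥ 7) = Σ C(10,x) pˣ(1−p)¹⁰⁻ˣ for x = 7 to 10.

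| True rate | Stated | Exact, ≥7/10 |
|---|---|---|
| 60% | 63% | 38.2% |
| 70% | 88% | 65.0% |
| 90% | 99% | 98.7% |

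Only the last figure reproduces. The stated 63% equals P(X ≥ 6) at 60% (63.3%), and the stated 88% equals P(X ≥ 7) at a true 80% (87.9%). This is a separate error in the same paragraph. The steps below use the exact values.

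**2. Precision.** The Clopper-Pearson limits are: lower = the 0.025 quantile of Beta(x, n−x+1); upper = the 0.975 quantile of Beta(x+1, n−x).

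| Result | 95% interval | Width (points) |
|---|---|---|
| 7/10 | 34.8% to 93.3% | 58.6 |
| 28/40 | 53.5% to 83.4% | 30.0 |
| 35/50 | 55.4% to 82.1% | 26.7 |

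The ratio of widths, 10 against 50 patients, is 58.6/26.7 = 2.2. Part II alone is already about twice as precise as Part I (58.6/30.0 = 2.0). The 28/40 and 35/50 rows hold the observed rate at 70% for comparison; they are not predictions. At an observed 80% the intervals are 44.4% to 97.5% (8/10) and 66.3% to 90.0% (40/50).

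**3. Effect of the gate on the estimates.** Given a pass, the mean Part I count is m = Σ x·P(X=x) / P(X ≥ 7), with both sums over x = 7 to 10. The expected Part I rate is m/10, and the expected pooled rate is (m + 40p)/50. At p = 0.60, m = 2.896/0.3823 = 7.57. The Part I rate is then 75.7% and the pooled rate (7.57 + 24)/50 = 63.1%.

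| True rate | P(pass) | Mean Part I rate, given pass | Mean pooled rate, given pass | Pooled bias (points) |
|---|---|---|---|---|
| 50% | 17.2% | 73.9% | 54.8% | 4.8 |
| 60% | 38.2% | 75.7% | 63.1% | 3.1 |
| 70% | 65.0% | 78.6% | 71.7% | 1.7 |
| 80% | 87.9% | 83.2% | 80.6% | 0.6 |
| 90% | 98.7% | 90.4% | 90.1% | 0.1 |

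The 40 Part II patients are enrolled after the gate, so their proportion carries no bias from it. At a true 35% the pooled bias would be 7.4 points, and the nominal 95% pooled interval would cover the truth about 86% of the time after a pass. The chance of passing at that rate is only 2.6%. At true rates of 60% to 90%, coverage after a pass is about 97%.

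**The case against.** The strongest reply is that Part I is openly a pilot. Sections 4.1 and 9 both call it a pilot study of feasibility, and the synopsis makes it the stop/continue step. A small go/no-go stage followed by an expansion cohort for correlative aims is a legitimate design. That stands, and the gate should be kept. What the reply does not cover is that Section 9 lets the gate double as the final answer on feasibility.

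The documents are also not uniform. The synopsis states the primary objective without limiting it to Part I, and nothing forbids scoring success in Part II. So this is an analysis left unstated, not one ruled out. That it can be done is my inference from Sections 3.3 and 4.2.

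Three stronger readings are tempting, and the documents do not support them.

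- A reader might infer that the trial's feasibility estimate is imprecise. The plan makes no estimate; the fault is that none is planned.
- A reader might infer that the Part II data go unused. They feed all three secondary aims and are missing only from the primary question.
- A reader might infer from the lower limit of 35% that a technique with so low a rate would readily be called feasible. At true rates of 35% and 40% the rule passes only 2.6% and 5.5% of the time. Discrimination is weak higher up: 17% pass at a true 50% and 38% at 60%.

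**Conclusion.** The point holds as a gap in the planned primary analysis; it does not invalidate the design. The primary objective is decided by a count in ten patients, with no proportion or interval. If the gate is passed, scoring the same endpoint in the patients already being imaged would cut the width of the exact 95% interval from about 59 to about 27 points at an observed 70%.

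This rests on four assumptions: a two-sided 95% level; the same observed rate in both parts, for illustration; the four-item endpoint of Sections 3.3 and 9; and scoring of Part II from the recordings that Section 4.2 already requires. The gain exists only if the gate is passed; otherwise ten evaluable patients are all the data. Nor would the planned 50 be everyone attempted: under Section 4.2, subjects with microscope malfunction or surgery ended for unrelated reasons go off-study and are replaced. The 50 are therefore evaluable patients, and the plan needs to say so.

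**What to change.** In Sections 3.1 and 9:

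1. Keep 7 of 10 as the continue/stop gate only, and reword the feasibility declaration to say that the study continues.
2. If the gate is passed, define the primary result as the success proportion with a two-sided 95% Clopper-Pearson interval over all evaluable patients in Parts I and II (planned 50).
3. Beside it, report the Part II patients alone (planned 40) as the estimate free of gate selection.
4. Add a sensitivity analysis over all attempted patients, with those replaced under Section 4.2 in the denominator as non-successes, and list the reasons for replacement.
5. If the gate is failed, report the Part I proportion with its exact interval.

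While that paragraph is open, correct the stated pass probabilities. Also reconcile the rule with the synopsis, whose mention of three or more patients could be read as stopping at exactly 7 successes and 3 failures.

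The cost is wording and a few lines of analysis, with no added patients, visits or procedures. The downside is the pooled estimate's upward bias: about 5 points at a true 50%, 3 at 60%, and under 2 at 70% and above. It is larger at lower true rates, where passing the gate is unlikely. Item 3 lets readers see past it.

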### 3.2 SECONDARY OBJECTIVES - PART II (40 PATIENTS):

1. Compare the microscopic observation of the tumor-associated vessels with normal tissue (peritoneal surface) in each individual subject.
2. Correlate the microscopic observations of the tumor-associated vessels with pathologic grade of tumor.
3. To correlate the microscopic observation of the microvasculature with tumor-specific and overall survival.

